Appendix 6: Additional data inclusion from other trials merged under ACTIV-4 platform

There are several clinical trials that have been testing safety and efficacy of Arm A and B regimens. Data collected in these trials will be included in the data analysis under this protocol provided that the subjects consented for the data to be shared or a waiver of consent and authorization had been granted by the reviewing IRB. The data will be labeled with subject ID and only include dates which are necessary to assess safety and efficacy endpoint events. All other private health information (PHI) will be removed. The data will be stored at the study coordinating center, University of Pittsburgh, in HIPAA compliant electronic system and only coordinating center staff will have access to the data. The statistical analysis plan will account for this additional data.

Appendix 7: Background and Rationale for Arm C: P2Y12 inhibitor for ICU Level of Care (Severe) Cohort

A7.1 Background and Rationale for Arm C

Analysis of therapeutic vs prophylactic dose anticoagulation in severely ill patients demonstrated that therapeutic dose anticoagulation was not superior, and there was a trend toward harm. Therefore prophylactic dose anticoagulation is considered standard of care for severely ill patients. The number of days with organ support or death over the first 21 days of the index hospitalization remained high despite standard of care treatment, and bleeding risk was < 2%. Therefore, additional antithrombotic and additional treatment strategies should be tested.

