5. **Study per protocol for P2Y12 and heparin.** This consists of the patients in the study confirmed unblinded population who have been treated as per protocol for P2Y12 and with the suggested dose of heparin anticoagulation according to illness severity at the time of randomization. In this analysis that is defined as 1) patients randomized to P2Y12 and who received at least 1 dose by day zero (day of randomization) or Day 1 (first full day after randomization, **and** 2) patients randomized to usual care who did not receive a P2Y12 dose on or by the end of first full study day after randomization (Day 1) , **and** 3) patients who received at least 1 dose of therapeutic anticoagulation by Day 1 if in moderate severity, or at least one dose of prophylactic anticoagulation by Day 1 if severe illness state.

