#### [12.10. Definition of times](#)

Adherence and per protocol analyses will rely on assessment of drug administration by the end of the first full study day after randomization. Post-randomization day 1 is referred to as study day 1 and constitutes the 24-hour period commencing at midnight of the day after randomization.

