#### [12.11. Post-randomization analyses](#)

Participants who are randomized to receive one strategy may in fact be treated with another strategy based on health status and provider discretion. Co-interventions during the treatment period (e.g., aspirin, corticosteroids, IL6 antagonists, anticoagulants and their dosing) may modify the benefit or harm of P2Y12. Exploratory analyses will estimate the causal effect of the treatment for these patients using marginal structural modelling techniques. These techniques use inverse probability weighting methods that are based on patient-level covariates to create comparable groups for the analysis.

Anticoagulant treatment will be classified as based on the following dosing equivalents categorization: (1) standard prophylactic, (2) intermediate prophylactic, (3) subtherapeutic, and (4) therapeutic. The criteria for each categorization for each anticoagulant are given in Appendix B. Based on sample size, may collapse groups for analyses

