## 12.12. Heterogeneity of treatment effect

The heterogeneity of the treatment effect will be evaluated in the following a priori defined subgroups:

- Age (< 50 years, 50-70 years, > 70 years)
- Sex
- Invasive mechanical ventilation at baseline for severe cohort
- For moderate (the amount of O2 required, no O2, > 0 but <= 2, >2)
- Heparin dosing during day 1. Categorized as therapeutic if defined as therapeutic at any time during day 0 or 1.

Additional exploratory subgroup analyses will include the following:

- Race/Ethnicity
- D-dimer levels
- Markers of inflammation (CRP, ferritin)
- Baseline troponin
- BMI
- Shock (use of vasopressors or inotropes at baseline)
- Baseline chronic kidney disease
- Steroid administration for COVID-19 at baseline
- IL-6 inhibitor administration for COVID-19 at baseline
- If additional treatments are determined through other research to be beneficial before unblinding subgroups will be defined by those treatments.
- Sites with at least 80% ticagrelor use as assigned P2Y12 inhibitor vs. sites with less than 80% ticagrelor use
- Geographic (Europe, US+Canada, Central and South America)

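### For severe patients, the P2Y12-and-heparin per-protocol set has a prophylactic-dose floor but no ceiling, so it can admit patients whom SAP 12.12 classes as therapeutic

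*SAP*

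**What the plan says.** SAP 6 item 5 describes its population as patients "treated as per protocol for P2Y12 and with the suggested dose of heparin anticoagulation according to illness severity at the time of randomization". The heparin part is then made operational by cohort. The moderate rule takes "patients who received at least 1 dose of therapeutic anticoagulation by Day 1 if in moderate severity". The severe rule takes "at least one dose of prophylactic anticoagulation by Day 1 if severe illness state". No further clause limits what else a severe patient may have received.

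On which dose is suggested for severe illness, Protocol A7.1 reports that in severely ill patients "therapeutic dose anticoagulation was not superior, and there was a trend toward harm" and concludes: "Therefore prophylactic dose anticoagulation is considered standard of care for severely ill patients". Protocol A7.4 also recommends prophylactic-dose anticoagulation alongside the P2Y12 inhibitor in Arm C.

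Two other SAP sections classify heparin exposure. SAP 12.11 uses four categories: "1) standard prophylactic, (2) intermediate prophylactic, (3) subtherapeutic, and (4) therapeutic". SAP 12.12, for the heparin subgroup, has the rule "Categorized as therapeutic if defined as therapeutic at any time during day 0 or 1".

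The window is fixed by SAP 12.10: "Adherence and per protocol analyses will rely on assessment of drug administration by the end of the first full study day after randomization".

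**The concern.** A one-dose rule behaves differently in the two cohorts. For moderate patients the suggested dose is the highest class, so a single therapeutic dose settles the matter. For severe patients it is a lower class, and a single prophylactic dose says nothing about whether a higher dose was also given. The severe rule can therefore admit the exposure that the set is meant to keep out.

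This matters because item 5 is the only population in SAP 6 that conditions on the anticoagulant background. SAP 12.11 itself allows that anticoagulants and their dosing may modify the benefit or harm of P2Y12, and it expects some patients to be treated with a strategy other than the assigned one. A sensitivity analysis of organ support-free days (OSFD) in this set would naturally be read as the effect of P2Y12 on prophylactic heparin in severe patients. Under the written rule, the background may be a mixture.

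**Working it through.** No sample size, power or error-rate figure is involved, and the plan gives no figure to reproduce. The check applies the two rules literally to the same patient.

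**Inputs.** SAP 6 item 5 (severe and moderate heparin criteria), SAP 12.12 (any therapeutic dosing on Day 0 or 1 counts as therapeutic) and SAP 12.10 (assessment ends with Day 1). P is a prophylactic dose and T a therapeutic dose, with one class per day for simplicity. The patient is assumed to have confirmed COVID-19, to belong to a cohort being reported and to meet the P2Y12 criterion.

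**Severe patient**

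| Day 0 / Day 1 | In item 5 set? | Therapeutic under 12.12? | Agree? |
|---|---|---|---|
| P / P | yes | no | yes |
| P / T | yes | yes | **no** |
| T / P | yes | yes | **no** |
| T / T | no | yes | yes |

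Two of four patterns count as the suggested dose in one section and as therapeutic in the other.

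**Moderate patient**

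| Day 0 / Day 1 | In item 5 set? | Therapeutic under 12.12? | Agree? |
|---|---|---|---|
| P / P | no | no | yes |
| P / T | yes | yes | yes |
| T / P | yes | yes | yes |
| T / T | yes | yes | yes |

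None of the four conflict.

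**Alternative reading.** If the severe rule were taken to mean prophylactic intensity or higher, T / T would also enter the set. Three of four severe patterns would then conflict, so this reading makes the mismatch larger.

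**After the change.** If severe patients qualify only when their highest class on Day 0-1 is prophylactic, only P / P enters, and the conflicts fall from 2 of 4 to 0 of 4.

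**Limits of the check.** These are counts of patterns, not of patients. Escalation after Day 1 is outside the conflict, because 12.12 does not look beyond Day 1 and 12.10 deliberately stops there. How item 5 treats intermediate and subtherapeutic doses cannot be checked, because the dose criteria sit in SAP Appendix B, whose content is not shown.

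**The case against.** The strongest reply is that the two rules serve different purposes. SAP 12.12 must place each patient in one subgroup, so it needs exclusive categories. Item 5 is an initiation criterion, in the same one-dose-by-Day-1 form as the P2Y12 criteria in items 4 and 5. That is fair as far as form goes, but item 5 states a purpose of its own, treatment with the suggested dose for the severity. The severe rule misses that purpose whatever 12.12 says.

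A second reply is that the matter is covered elsewhere. SAP 10 compares anticoagulant drug and dose between arms, 12.11 plans exploratory marginal structural models, and 12.12 separates out therapeutic dosing. These would help to reveal a mixed background, but they do not change who is in the set. Item 4 is a second per-protocol set with no heparin criterion, so the P2Y12 per-protocol question does not depend on item 5.

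A third reply stands and has to be carried into the fix. Protocol 6.2 names thrombotic events and clinical worsening as reasons for changing strategy. Excluding severe patients escalated by Day 1 may remove some because of an early outcome event or deterioration, and this could differ by arm.

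A reader might go further and infer that, because treatment is open label, clinicians would escalate heparin less often in P2Y12 patients, so that this set would make P2Y12 look safer on bleeding. The documents do not support that. No visible text specifies a bleeding analysis on this set: the outline in SAP 13.1 covers only OSFD, the bleeding tables in the safety monitoring plan name no per-protocol set, and the per-protocol entries left in the SAP table of contents do not include bleeding. Nor do the documents give an escalation rate by arm or a bleeding rate for severe patients given therapeutic heparin, so neither the direction nor the size of any bias can be derived.

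**Conclusion.** The point holds as a mismatch between a stated purpose and the rule that implements it, limited to the severe cohort and to dosing on Day 0-1. It is minor. The primary analysis is intention-to-treat, the superiority and futility triggers do not use this set, and Protocol 8.5 gives per-protocol work a supporting, sensitivity role. The effect is on interpretation: results from this set in severe patients cannot be described as P2Y12 on the suggested heparin dose without qualification. If mixed dosing proves equally common in both arms, the comparison need not be distorted, but the set still does not represent the regimen it names.

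The conclusion rests on a literal reading of item 5 and 12.12, and on prophylactic being the suggested dose for severe illness as Protocol A7.1 and A7.4 state. The number of affected patients is unknown and could be small. The point concerns analysis classification only and takes no position on which dose is clinically right.

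**What to change.** Reconcile item 5 with 12.12 by rewriting criterion 3 for the severe cohort in terms of the highest anticoagulant dose class received on Day 0-1. A patient whom 12.12 classes as therapeutic would then not be counted as on the suggested dose. State which of the 12.11 categories count as prophylactic for this purpose, in particular whether the intermediate category does. Leave the moderate rule and the Day 1 window as they are.

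The cost is one sentence in the SAP, using dose classes already planned under 12.11, and it should be settled before unblinding. The set will be somewhat smaller. Because some exclusions may follow an early thrombotic event or deterioration, report the number of severe patients excluded by the new condition, by arm and with the reason, and present the result under the current rule next to the revised one. If the two agree, the choice of rule does not matter; if they differ, the exclusion table helps the reader judge whether dosing or selection is the likelier cause.

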## 7. Endpoints

The following endpoints will be analyzed, displayed graphically, and summarized with descriptive statistics.

1. **Organ Support-Free Days (OSFDs)**
  - This is the primary endpoint for the study, and is a composite ordinal endpoint reflecting the number of days alive and off organ support, with in-hospital mortality from any cause as the worst possible outcome. Organ support considered is cardiovascular (vasopressor/inotrope support) and respiratory support (high flow nasal cannula, invasive or non-invasive ventilation, or ECMO).

In-hospital death is considered a -1 and may occur after study day 21 as long as it occurs during the index hospitalization through day 90.

- Detailed definitions for OSFDs are specified in the study data dictionary.
- Missing values for organ support-free days will be treated as “missing and will not be included in the analyses”. We will conduct a sensitivity analysis on the primary endpoint treating missing values using the “last known status carried forward” approach.

## 2. **In-Hospital Mortality**

- A dichotomous endpoint of in-hospital death from any cause where the death component corresponds to a -1 on the OSFD endpoint. The measurement of in-hospital mortality is truncated at 90 days.

## 3. **28-day Mortality**

- A dichotomous endpoint of death from any cause. The measurement of mortality is not dependent on the location of the patient.

## 4. **Mortality**

- This is a time-to-event endpoint through 90 days.
- Any patient currently in the hospital or transferred on organ support to an alternative care facility will be censored at their last known status alive, regardless of location at the time of that last assessment.
- Any patient successfully discharged from hospital, alive, without organ support, will be censored at the date of discharge if 90-day mortality data are not yet recorded.

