7.1 Study Schedule

Activity	Screening/ Enrollment	Hospital Duration	28 days and/or hospital discharge***	90-days post randomization and longer term follow-up
Eligibility				
Consent	X			
Demographic and Medical History	X			
Assessment of Inclusion/Exclusion criteria	X			
Self-reported race/ethnicity and gender	X			
Study Drug Administration				
Randomization	X			
Study treatment	X	X		
Study Procedures				
Height	X			
Weight	X			
Vital signs	X			
Concomitant medications	X	X		
WHO ordinal assessment	X	X	X	X
Quality of Life and Functional Status [#]	X			X
Outcomes Assessment [#]		X	X	X
SOC Laboratory Assessments				
Chemistry panel	X	X	X	
Hematology panel	X	X		
D-dimer*	X			
Blood Group**	X			

See arm-specific appendices for additional measures

*D-dimer is strongly recommended for measurement in all participants as close to the time of randomization as feasible.

**Blood group will come from hospital record or self-report if available. Biospecimens see appendix 4.

***Assessments indicated in the table above will be ascertained at discharge, or at 28 days, whichever comes first. Participants must be followed for vital status until discharged from the hospital or another care facility (if transferred on organ support) up to 90 days. To maximize retention, participants will be contacted intermittently post-discharge and that contact will be recorded in the EDC.

#Participants may be assessed for functional status and quality of life that reflects baseline status pre-COVID illness and functional and vital status and quality of life at 90 days and longer-term follow-up (Instruments detailed in the manual of operations). Participants may be contacted in the future, including after this study is over to collect information about their health status (e.g. quality of life, functional and vital status) and ascertain their interest in other studies about COVID-19.

Laboratory Procedures/Evaluations

See arm-specific appendices.

All analyses will be performed on SOC labs and procedures done for usual care. The standard operating procedures for samples to be collected for research purposes are included as Appendix 5. All research samples will be timed with clinical lab draws to limit provider exposure. Collection of research samples as outlined in Appendix 5 is strongly encouraged where safe and feasible.

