#### 3.1. Reporting strategy

This SAP describes the planned analyses for the study. As outlined below, two cohorts (moderate illness, severe illness) may report at different times. Multiple reports describing the results of analysis may be prepared and published to ensure expedited dissemination of the study findings. It is anticipated that for each cohort, expedited, potentially preliminary reports will describe key primary and secondary findings and limited subgroup analyses.

Endpoints to be reported in these reports include:

- Organ support-free days to day 21 (primary endpoint)
- In-hospital mortality (key secondary endpoint)
- Major thrombotic events or death (key secondary endpoint)
- ISTH major bleeding (key safety endpoint)

Comprehensive reports providing complete characterization of trial results may subsequently be prepared and published.

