#### 12.4. Analytic Approach for Secondary Time-To-Event Endpoints

All inferential time-to-event analyses will be done using a Bayesian piecewise exponential model. The Bayesian time-to-event model is intended to mirror a Cox proportional hazards model, with the underlying hazard rate modeled with a piecewise exponential model. The underlying hazard will be modeled with a hazard rate for each 10-day period in the model. The prior distribution for the hazard rate for each day is a gamma distribution with 1 day of

exposure and a mean equal to the total exposure divided by the total number of events. This prior will have very little weight but will provide numerical stability to the model. Each factor is incorporated as a proportional hazard rate through an additive linear model of the log-hazard. The default prior for each factor is the same as for the log-odds in the ordinal model. If other non-specified variables are added to the model, then a normal distribution with mean 0 and standard deviation 10 will be utilized.

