#### [12.9. Handling of missing data](#)

For the primary endpoint of OSFDs missing primary outcomes will be ignored. A sensitivity analysis is conducted where last status carried forward is used for imputation. Patients with missing age, date of randomization, sex or treatment assignment will be ignored. For additional endpoints those patients missing the endpoint will be ignored (for time to event analyses censoring will be used and aren't considered missing). For the subgroup analyses patients with missing subgroup variables will be lumped into a single group of "missing" in addition to the subgroup classifications.

For time-to-event analyses patients that have a competing event that dictates they cannot achieve a positive outcome (like death for time to hospital discharge), the patient will be assigned a no positive event outcome at the maximum time for the analysis. Patients not achieving an absorbing event that become lost-to-follow up will be censored at the last known time (unless otherwise specified for the analysis).

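### Time-to-event mortality censors recovered patients at discharge while day-90 status is pending, which overstates Kaplan-Meier mortality and may shift the hazard ratio either way

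*SAP*

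**What the plan says.** SAP section 7, endpoint 4 defines mortality with the words "This is a time-to-event endpoint through 90 days" and gives two censoring rules.

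- A patient still in hospital, or transferred on organ support, "will be censored at their last known status alive, regardless of location at the time of that last assessment".
- A patient discharged alive without organ support "will be censored at the date of discharge if 90-day mortality data are not yet recorded".

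The general rule in SAP 12.9 is that patients who "become lost-to-follow up will be censored at the last known time (unless otherwise specified for the analysis". The endpoint 4 rule is such a specification, so it overrides the default.

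On the model, SAP 12.4 states: "All inferential time-to-event analyses will be done using a Bayesian piecewise exponential model". SAP section 8 allows Kaplan-Meier or cumulative incidence plots without choosing between them. No sensitivity analysis is listed for this endpoint.

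Two other places bear on how often the rule will apply. Protocol 7.1 says that "participants will be contacted intermittently post-discharge and that contact will be recorded in the EDC", so alive dates later than discharge can exist. SAP 3.1 foresees that "expedited, potentially preliminary reports will describe key primary and secondary findings", so an analysis may be run while day-90 status is still outstanding for recent enrollees.

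**The concern.** The piecewise exponential model and the Kaplan-Meier estimator both assume that a censored patient has the same future risk as those who stay under observation. A patient who has left hospital alive and off organ support is at lower risk than one still in a bed. If such patients leave the risk set at discharge, the remaining inpatients stand in for them and the estimated hazard is too high.

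The rule also treats the groups unequally. The patients with the best prognosis are the only ones whose known survival time after discharge is discarded. SAP 12.9 deals with the mirror problem: where death prevents a good outcome such as discharge, "the patient will be assigned a no positive event outcome at the maximum time for the analysis". Nothing comparable protects the mortality analysis from discharge.

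At stake is the credibility of a reported 90-day mortality curve and, to a lesser degree, of its hazard ratio. All-cause mortality at 90 days is a listed secondary endpoint in Protocol 4.2.2. Endpoint 4 is the SAP endpoint that measures death in any location to day 90.

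**Working it through.** The documents give no death rate, discharge rate or pending share for this endpoint, so there is no stated figure to reproduce. All rates below are assumptions. The 90-day horizon, the censoring rule and the 10-day hazard pieces come from the SAP.

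**Set-up.** Let d be the daily death hazard in hospital, g the daily discharge hazard, q the daily death hazard after discharge, and p the share of discharged patients whose day-90 status is pending.

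- Still in hospital: I(t) = exp(−(d+g)t)
- Discharged and alive: D(t) = g·[exp(−qt) − exp(−(d+g)t)] / (d+g−q)
- True mortality at day 90: 1 − I(90) − D(90)
- Hazard seen under the rule: h(t) = [d·I + q(1−p)·D] / [I + (1−p)·D]
- Kaplan-Meier mortality under the rule: 1 − exp(−∫h dt), from 0 to 90

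Assumed severe cohort: d = 0.012, g = 0.04, q = 0.0004. Assumed moderate cohort: d = 0.008, g = 0.10, q = 0.0004.

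**One point in time, severe, day 30.** I = 0.210 and D = 0.603.

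- True hazard: (0.012×0.210 + 0.0004×0.603)/(0.210 + 0.603) = 0.0034 per day.
- With 30% pending: (0.012×0.210 + 0.0004×0.7×0.603)/(0.210 + 0.7×0.603) = 0.0043 per day.

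**Kaplan-Meier mortality at day 90.**

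| Pending share of discharged | Severe | Moderate |
|---|---|---|
| 0% (true) | 0.250 | 0.104 |
| 15% | 0.265 | 0.109 |
| 30% | 0.283 | 0.116 |
| 60% | 0.337 | 0.137 |
| 100% | 0.660 | 0.513 |

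At 100% pending only inpatients remain, so the severe value is 1 − exp(−0.012×90) = 0.660. A simulation of 400,000 patients per arm gives the same values to within about 0.001, except about 0.50 for moderate at 100%, where few patients remain at risk. If post-discharge deaths are recorded at once and only survivors stay pending, 30% pending gives 0.290 (severe) and 0.128 (moderate).

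**Hazard ratio.** This is death, P2Y12 versus control, so below 1 is benefit; the SAP reports the inverse. Values are simulated with the 10-day piecewise model, fitted by maximum likelihood.

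| Scenario | 0% pending | 30% | 60% | 100% |
|---|---|---|---|---|
| Severe, discharge hazard ×1.2 only | 0.881 | 0.890 | 0.906 | 0.996 |
| Severe, in-hospital death hazard ×0.8 only | 0.829 | 0.824 | 0.818 | 0.797 |
| Severe, both | 0.733 | 0.735 | 0.741 | 0.800 |
| Moderate with q = 0.0015, in-hospital death ×0.8 only | 0.918 | 0.900 | 0.869 | 0.802 |

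With identical arms there is no bias at any pending share, since both arms have the same hazards and lose the same patients (simulated 1.003 to 1.004, severe). As the pending share rises, the estimate drifts from the 90-day hazard ratio toward the ratio among patients still in hospital. That explains why benefit is hidden in the first row and overstated in the second.

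**A second model.** This assumes 25% in-hospital deaths with Weibull times, 3% post-discharge deaths and lognormal discharge with median 12 days. True mortality is 27%.

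- Kaplan-Meier mortality reads 30%, 31%, 35% and 83% at 20%, 30%, 50% and 100% pending.
- With no mortality effect and discharge times cut by 25%, the hazard ratio is 1.01, 1.03, 1.05 and 1.31.

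**A realistic snapshot.** Assume 300 days of uniform accrual, so 90/300 = 30% of patients have under 90 days of follow-up when the last patient enrolls, and a treatment that raises the discharge hazard by 20%. At that snapshot the severe control arm reads 0.274 under the rule against a true 0.252. Censoring at the snapshot with current vital status gives 0.252. The hazard ratio is 0.892 under the rule, 0.883 with snapshot censoring and 0.878 with full follow-up. With the snapshot 90 days after last enrollment, all three methods agree.

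**The case against.** The strongest reply is that the rule is conditional and temporary. Vital status is collected at day 90 (Protocol 7.1.3) and Protocol 8.5.2 expects very good retention, so at a final analysis only patients never reached would be affected. This stands, and it confines the point to early analyses and that residual group.

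Second, the endpoints that SAP 3.1 names for expedited reports include in-hospital mortality, which has no discharge censoring, and not time-to-event mortality. This also stands in part. The list is worded as what the reports include, so it does not exclude endpoint 4, but neither does it promise it.

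A reader might infer that the rule will make a useful drug look harmful. The documents do not support that. They give no discharge or death rates, and the direction depends on which of the two the treatment changes. A large distortion, such as 1.31, needs every discharged patient to be pending, which implies a snapshot within about 90 days of first enrollment.

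A reader might also infer that the trial's conclusions are at risk. They are not: the superiority and futility triggers in SAP 4.4 and 12.13 rest on OSFD alone.

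**Conclusion.** The point holds as a defect in one secondary endpoint. Before day-90 follow-up is complete, and for patients never reached, censoring at discharge is informative and overstates Kaplan-Meier mortality. The direction needs only a lower death hazard after discharge than in hospital, which is an assumption but a natural one. The size rests on assumed rates: from a true 25–27% to about 28–31% with 30% pending, and to about 34–35% with 50–60% pending.

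The hazard ratio is a lesser matter. Its bias is nil when the arms do not differ, about 0.03 or less at up to 30% pending, possible in either direction, and large only when most discharged patients are pending. The change is worth making because it is cheap and brings endpoint 4 into line with SAP 12.9.

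**What to change.** - **Censoring date.** Replace the third bullet of SAP section 7, endpoint 4. Patients discharged alive without organ support and without day-90 status should be censored at the latest date recorded alive, including post-discharge contacts in the EDC. This follows the last-known-time default in SAP 12.9.
- **Timing.** Before follow-up is complete, run time-to-event mortality only in patients randomized at least 90 days before the snapshot. This matters because a patient with no contact after discharge would still be censored at discharge, and because deaths may be recorded sooner than survival.
- **Sensitivity analysis only.** Carry patients with no post-discharge contact as alive to the earlier of the snapshot or day 90. This should not be the main rule. Protocol Appendix 2 assumes freedom from organ support after discharge, and only to day 21; it does not assume survival to day 90, and doing so could understate mortality.

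The cost is a change of SAP wording, one derived date from data already collected, and fewer patients in preliminary mortality analyses.
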